2 LIST OF ABBREVIATIONS AND DEFINITIONS OF TERMS

Abbreviation	Term
AChEI	acetylcholinesterase inhibitor
AE	adverse event
ATC	anatomical therapeutic class
BMI	body mass index
BP	Blood pressure
C-CASA	Columbia Classification Algorithm for Suicide Assessment
CI	confidence interval
CIBIC-Plus	Clinician's Interview Based Impression of Change Plus Caregiver Input
CFI	Cognitive Fluctuation Inventory
CGIC	Clinician Global Impression of Change
cGMP	cyclic guanosine monophosphate
CRF	case report form
CSF cGMP	cerebrospinal fluid
CSR	clinical study report
C-SSRS	Columbia Suicide Severity Rating Scale
CV	coefficient of variation
DBP	Diastolic blood pressure
DLB	Dementia in Lewy Bodies
ED	Early Discontinuation
FAQ	Functional Assessments Questionnaire
FAS	full analysis set
LLT	lower level term
LS	least squares
MDS	Movement Disorders Society
MedDRA	Medical Dictionary for Regulatory Activities
MMSE	Mini-Mental State Examination
MoCA	Montreal Cognitive Assessment
NPI	Neuropsychiatric Inventory

Abbreviation	Term
NPI-D	Neuropsychiatric Inventory – Distress symptoms
PD	pharmacodynamic
PDD	Parkinson's Disease Dementia
PK	pharmacokinetic
PT	Preferred term
QTcB	corrected QT interval calculated using Bazett's formula
QTcF	corrected QT interval calculated using Fridericia's formula
RBD	REM sleep behavior disorder
SAE	serious adverse event
SAP	statistical analysis plan
SAPS-PD	Scale for Assessment of Positive Symptoms in Parkinson's Disease
SBP	Supine blood pressure
SE	standard error
SI	Système International
SOC	System organ class
TEAE	treatment-emergent adverse event
TEMAV	treatment-emergent markedly abnormal laboratory value
TLG	tables, listings, and graphs
UPDRS-III	Unified Parkinson's Disease Rating Scale Part III: Motor Examination
WAIS-IV DSC	Wechsler Adult Intelligence Scale-4th Edition Digit Symbol Coding
WHO	World Health Organization
WHO DD	World Health Organization Drug Dictionary

Table 1 Summary of Changes (Version 2)

Changes in Version 2	Rationale

5.2.1 Definitions of Analysis Sets
 
Addition to the definition of subjects being excluded from the PD Analysis Set, based on low drug compliance/PK concentrations at Week 9.
	
Subjects with low PK concentrations, and therefore low drug compliance at Week 9 had outlying cGMP percentage change from baseline values. This was not helpful in determining proof of concept and hence they are to be excluded from the PD Analysis Set, and kept in all other analysis sets.


5.2.4 Demographic and Other Baseline Characteristics and 5.3.4 Examination of Subgroups
 
Update to cutpoint for CSF Aβ42/40 ratio and CSF p-tau181/Aβ(1-42) ratio
	
In correct cutpoints were referenced. CSF Aβ42/40 ratio was changed from 0.0597 to 0.0571. CSF p-tau181/Aβ(1-42) ratio was changed from 0.0749 to 0.083.

5.3.4 Examination of Subgroups and 5.6.2 Adverse Events
 
Removal of subgroups for: On AChEI at baseline (Yes or No), Hoehn & Yahr stage (0&I&II or III), Baseline MMSE subgroup (\geq14 total score \leq19, \geq20 total score \leq26), Age ($<$65, \geq 65), NPI hallucination sub-item score (\geqmedian/$<$median), Caregiver's time per week to spend with subject (\geqmedian/$<$median).
	
Due to the number of subjects, it was not useful to subgroup the data in this detail.

8.2.3 Duplicate PD Tests
 
Wording added to implement derivation for any duplicate PD tests received.
	
Added for completion for derivation of a single value if duplicate tests received.

8.3.2 Treatment Duration for Safety Analyses
 
Footnote d added to Table 5
	
Footnote d added for clarity.

8.4 Algorithms for Efficacy Parameters
 
NPI total scores are set to zero if any part
	
To be consistent with the derivation from Study 201

is missing, changed from set to missing if any part is missing.	
---	--

3 INTRODUCTION

The purpose of this statistical analysis plan (SAP) is to describe the procedures and the statistical methods that will be used to analyze and report results for Eisai E2027-A001-203.

3.1 Study Objectives

3.1.1 Primary Objective

The primary objective of the study is to demonstrate the Pharmacodynamic (PD) effects of E2027 on cerebrospinal fluid (CSF) cyclic guanosine monophosphate (cGMP) in subjects with dementia with Lewy bodies (DLB) and Parkinson's disease dementia (PDD) with and without amyloid copathology after 9 weeks of treatment.

3.1.2 Secondary Objective

The secondary objective of the study is to evaluate the safety and tolerability of E2027 in subjects with DLB and PDD.

3.1.3 Exploratory Objectives

The exploratory objectives of the study are:

- To evaluate the efficacy of E2027 on the following endpoints after 12 weeks of treatment:
 - Montreal Cognitive Assessment (MoCA)
 - Wechsler Adult Intelligence Scale-4th Edition Digit Symbol Coding (WAIS-IV DSC)
 - Clinician's Interview Based Impression of Change Plus Caregiver Input (CIBIC-Plus)
 - Clinician Global Impression of Change (CGIC)
 - Cognitive Fluctuation Inventory (CFI)
 - Mini-Mental State Examination (MMSE)
 - Neuropsychiatric Inventory (NPI)
 - Scale for Assessment of Positive Symptoms in Parkinson's Disease (SAPS-PD)
 - Functional Assessments Questionnaire (FAQ)
- To explore the indirect PD effects of E2027 on plasma biomarkers and CSF biomarkers related to DLB and PDD
- To explore the effects of E2027 on CSF cGMP, other plasma and CSF biomarkers, and clinical endpoints using other diagnostic subgroups classifications based on baseline biomarkers
- To characterize the population pharmacokinetics (PK) of E2027 in subjects with DLB or PDD, including evaluation of the effects of intrinsic and extrinsic factors on the PK

- To explore the relationships amongst the PK exposure of E2027 in plasma/CSF and its effects on plasma/CSF biomarkers (including CSF cGMP) as well as clinical efficacy and safety endpoints
- To explore the relationship amongst plasma and CSF biomarkers at baseline and after treatment with E2027
- To collect genomic samples for exploratory investigation on heterogeneity in drug-response and clinical features of disease.

3.2 Overall Study Design and Plan

This is a multicenter, open-label study in subjects with DLB or PDD who were treated with E2027 for 12 weeks. Four subgroups of subjects were enrolled as follows: DLB without amyloid copathology, DLB with amyloid copathology, PDD without amyloid copathology, and PDD with amyloid copathology. The presence of amyloid copathology was defined as ratio of plasma concentration of A β 42/A β 40 <0.092 (based on the C2N PreclivityAD assay).

The study design allowed for add-on therapy of E2027 to standard of care for DLB and PDD, which includes acetylcholinesterase inhibitors (AChEI) and/or memantine at stable doses, except for any prohibited medications specified in this protocol. Subjects who were not receiving AChEI or memantine were also eligible to participate in this study but were not permitted to start such medications during the study. It was required that in each subgroup there was to be at least 1 subject who was not receiving AChEI or memantine during the study. Subjects were required to be on stable doses of medications prescribed for the treatment of Parkinson's disease, maintained without change during the study.

For all subjects, study participation comprised 2 phases: Pretreatment Phase and Treatment Phase. The Pretreatment Phase included a Screening Period and a Baseline Period. The Treatment Phase included a Treatment Period and Follow-up Period. An overview of the study design is presented in Figure 1.

[figure not shown]

Figure 1 Study Design for Study E2027-A001-203

QD = once daily, Sd = Start of study drug (E2027)

All subjects who have completed screening assessments and are deemed eligible for the study will have a baseline CSF. During the Treatment Period study visits were conducted after 3, 6, 9, and 12 weeks on E2027. Efficacy assessments were performed after 6 and 12 weeks on E2027. After subjects completed 9 weeks of treatment with E2027, a 2nd CSF sample was collected.

Subjects who prematurely discontinued study drug for any reason underwent an Early Discontinuation (ED) Visit within 7 days of their final dose of study drug. The safety and efficacy assessments normally performed after 12 weeks of treatment were conducted at the ED Visit. In addition, subjects who discontinued study drug were expected to continue in the study for the originally scheduled visits, starting with next such visit that was >7 days after the ED Visit.

During the COVID-19 pandemic, and under other extenuating circumstances:

- An extension of the Screening Period from 6 weeks to up to 10 weeks was allowed with sponsor approval on a subject by subject basis.
- If subjects could not visit the study site, all procedures which required physical contact with the subjects (eg, vital signs, ECGs, blood tests, physical examination, Unified Parkinson's Disease Rating Scale Part III: Motor Examination [UPDRS-III]) could be conducted via home visit (if feasible) with sponsor approval. The brain or cardiac imaging during the Screening Visit was to be conducted at the study site. The CSF collection at the Screening Visit and Visit 6 (Week 9) was to be conducted at the study

site. Other study procedures including all the efficacy endpoints, adverse events (AEs), and concomitant medications review could be conducted remotely via telephone, sponsor approved telehealth, or home visit. If it was not possible for subjects to attend the study site for the CSF collection Visit 6 (Week 9), this could be performed at an Unscheduled Visit as soon as possible after Week 9. Study drug was to be delivered to subjects' homes if it was not possible to visit the study site to collect the study drug.

4 DETERMINATION OF SAMPLE SIZE

Assuming the standard deviation of percentage change from baseline in CSF cGMP at Week 9 was 60, the sample size of 6 completers per subgroup (for 8 enrolled subjects per subgroup, assuming a 25% dropout rate), would have approximately 80% power to detect the difference in change from baseline of CSF cGMP of 100% between the DLB without amyloid copathology subgroup and the DLB with amyloid copathology subgroup. The analysis between the PDD without amyloid copathology subgroup and the PDD with amyloid copathology subgroup, also would have approximately 80% power to detect the difference in change from baseline of CSF cGMP of 100% (same assumptions as above). These sample size calculations illustrated the possible differences that could be seen between subgroups. However, without previous data on the differences between subgroups in CSF cGMP, these were for illustration only and it was not expected statistical significance would be reached with 6 subjects per subgroup.

The probability of observing a difference in percentage of CSF cGMP between 2 subgroups (DLB without amyloid copathology subgroup minus DLB with amyloid copathology subgroup, or PDD without amyloid copathology subgroup minus PDD with amyloid copathology subgroup) $\geq 30\%$ depends on the true difference between the 2 subgroups. If the true difference was 100%, there would be 97.8% probability that the observed difference was $\geq 30\%$. If the true difference was 60%, the probability was 80.7%. If the true difference was 10%, there would be 28.2% probability that the observed difference was $\geq 30\%$.

5 STATISTICAL METHODS

All descriptive statistics for continuous variables will be reported using mean, standard deviation (SD), median, minimum, maximum and number of subjects with non-missing data. Categorical variables will be summarized as number (percentage) of subjects.

5.1 Study Endpoints

5.1.1 Primary Endpoint

Percentage change from baseline in CSF cGMP at 9 weeks of treatment.

5.1.2 Secondary Endpoints

- Safety and tolerability of E2027 as measured by the following:
 - Incidence of adverse events including severe AEs, serious AEs, AEs resulting in discontinuation

- Incidence of orthostatic hypotension and orthostatic tachycardia
- Incidence of markedly abnormal laboratory values and shifts from baseline of laboratory values
- Incidence of abnormal ECG parameters and abnormal ECG findings
- Incidence of suicidality based on Columbia Suicide Severity Rating Scale (C-SSRS)
- Changes from baseline in the total score of MDS-UPDRS-III

5.1.3 Exploratory Endpoints

- The following clinical efficacy endpoints at 12 weeks of treatment
 - Change from baseline in MoCA total score
 - Change from baseline in WAIS-IV DSC score
 - CIBIC-Plus scale
 - CGIC scale
 - Change from baseline in CFI score
 - Change from baseline in MMSE total score
 - Change from baseline in NPI total score, subscores and caregiver distress score
 - Change from baseline in SAPS-PD total score
 - Change from baseline in FAQ total score
- Change from baseline in CSF cGMP at 9 weeks of treatment
- Percentage change and change from baseline at 9 weeks of treatment in other biomarkers in CSF and/or plasma, including using other diagnostic subgroups classifications based on baseline biomarkers (if appropriate)
- PK of E2027 in subjects with DLB or PDD, using population modelling
- Relationships between E2027 in plasma/CSF and its effects on the following variables using PK/PD modelling, if data permit:
 - Plasma/CSF PD biomarkers (including CSF cGMP),
 - Clinical efficacy (including MoCA, WAIS-IV DSC, CIBIC-Plus, NPI, MMSE, CFI, SAPS-PD, FAQ, and CGIC at 12 weeks of treatment),
 - Safety variables
- Relationships of the plasma and CSF PD biomarkers compared to MoCA, WAIS-IV DSC, CIBIC-Plus, NPI, MMSE, CFI, SAPS-PD, FAQ, and CGIC at 12 weeks of treatment, if data permit
- Relationships amongst plasma biomarkers and CSF biomarkers at baseline and after treatment (if appropriate)
- Subgroup analyses based on genotype classification for CSF cGMP changes from baseline and clinical endpoints

5.2 Study Subjects

5.2.1 Definitions of Analysis Sets

The Safety Analysis Set is the group of subjects who receive at least 1 dose of study drug and have at least 1 post baseline safety assessment.

The Full Analysis Set (FAS) is the group of subjects who receive at least 1 dose of study drug and have baseline and at least 1 post baseline MoCA measurement.

The PD Analysis Set is the group of subjects who have sufficient PD data to derive at least 1 PD parameter. Subjects who have low drug compliance based on their PK results will be excluded from the PD Analysis Set. Lack of drug around the Week 9 CSF will affect the results of the CSF cGMP, and hence distort the primary endpoint interpretation.

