9.1.2.1 Treatment Period

After completing study assessments at the Baseline Visit, subjects who continue to be eligible will proceed to the Treatment Period on E2027 (50 mg QD). They will be provided with E2027 to start administration in the morning of Day 1 at home. They will continue to take study drug for 12 weeks. During the Treatment Period study visits will be conducted after 3, 6, 9, and 12 weeks on E2027. Efficacy assessments will be performed after 6 and 12 weeks on E2027 and should be performed at approximately the same time of the day as at the Baseline Visit whenever possible (preferably in the morning). The MoCA should be the first efficacy assessment to be administered, followed by the WAIS-IV DSC (after 12 weeks only), then the CIBIC-Plus and finally the MMSE (after 12 weeks only). Whenever possible, a subject should have the same rater administering the MoCA and the CIBIC-Plus throughout his/her participation in the study. The rater administering the CIBIC-Plus should be independent of the rater(s) who administer the other clinical scales. The caregiver or informant will also complete the CIBIC-Plus, NPI, CFI, SAPS-PD (after 12 weeks only) and FAQ (after 12 weeks only). Safety assessments will be conducted at these visits, including review of AEs, vital signs, ECG, laboratory safety tests, C-SSRS, and UPDRS-III. The investigator will review all the efficacy endpoints and safety data at the visits after 6 and 12 weeks on study drug and formulate the CGIC of the subject's clinical status from baseline.

After subjects have completed 9 weeks of treatment with E2027 will have a 2nd CSF sample collected. The CSF sample will be collected in the morning at approximately the same time as at Screening, either in the fasted state or at least 2 hours after breakfast. A 2nd plasma sample for biomarkers will also be collected.

If during the study, the designated caregiver or informant relinquishes his/her responsibilities as caregiver or informant, a replacement caregiver or informant must be found. It is

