9.3.3 Removal of Subjects From Therapy or Assessment

The investigator may withdraw the subject from the study at any time for safety or administrative reasons. The subject may stop study drug or withdraw from the study at any time for any reason.

Subjects who prematurely discontinue study treatment for any reason will undergo an Early Discontinuation (ED) Visit within 7 days of their final dose of study treatment. The safety and efficacy assessments normally performed after 12 weeks of treatment will be conducted at the ED Visit. In addition, subjects who discontinue study treatment are expected to continue in the study for the originally scheduled visits, starting with next such visit that is >7 days after the ED Visit. Subjects who prematurely discontinue the study should attend at

least 1 originally scheduled visit after the ED Visit. At these originally scheduled visits that take place after the ED Visit, blood PK samples, plasma biomarker samples, and CSF samples will not be collected.

The primary reason for discontinuation and all other reason(s) contributing to the subject's discontinuation from study treatment should be collected. If a subject discontinues study treatment and the study at the same time, the end-of-study procedures (Final Visit) will be followed (see Section 9.5.5).

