9.7.1.6 Efficacy Analyses

The exploratory efficacy endpoints will be summarized based on the FAS, by subject subgroup (DLB without amyloid copathology, DLB with amyloid copathology, PDD without amyloid copathology, and PDD with amyloid copathology).

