5.3.5 Handling of Missing Data, Dropouts, and Outliers

5.3.5.1 Efficacy

For the efficacy endpoints, there will be no imputation of missing value.

Post-ED data will be included in all the analyses.

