5.8 Exploratory Analyses

The exploratory efficacy endpoints, MoCA (and subitems), WAIS-IV DSC, CIBIC-Plus (and subitems), CGIC, CFI, MMSE, NPI (NPI-12, NPI-10, NPI-4 and NPI-D, and each subscore), SAPS-PD and FAQ, will be summarized based on the FAS, by subject subgroup (DLB without amyloid copathology, DLB with amyloid copathology, PDD without amyloid copathology, and PDD with amyloid copathology). No formal statistical analyses will be performed. Figures will be produced by visit, they will present without amyloid DLB, with amyloid DLB, without amyloid PDD, with amyloid PDD, with amyloid and without amyloid copathology (regardless of DLB/PDD).

The exploratory efficacy endpoint, MoCA will be repeated for subgroups as per Section 5.3.4.

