8.4 Algorithms for Efficacy Parameters

This section describes the algorithms and missing data handling procedure to derive the totals scores for the efficacy parameters MoCA, NPI, MMSE, CFI, WAIS-IV DSC, SAPS-PD and FAQ.

Montreal Cognitive Assessment (MoCA)

This scale assesses different cognitive domains: attention and concentration, executive functions, memory, language, visuoconstructional skills, conceptual thinking, calculations, and orientation. It is reported to be useful to characterize global cognitive impairment in DB. The MoCA scale is composed of 11 assessments. The following are the assessments and possible points earned for each assessment:

Visuoconstructional skills (0 – 5 points), Naming (0 – 3 points), Memory (No points), Attention: Forward/backward digit span (0 – 2 points), Attention: Vigilance (0 – 1 point), Attention: Serial 7s (0 - 3 points), Language: Sentence repetition (0 – 2 points), Language:

Verbal fluency (0 – 1 points), Abstraction (0 – 2 points), Delayed recall (0 – 5 points), and Orientation (0 – 6 points).

The MoCA Total Score (range 0 to 30) = sum of all points earned. If any assessment is missing, then the Total Score is missing. The lower the total score, the worse the cognitive impairment.

Clinician's Interview Based Impression of Change Plus Caregiver Input (CIBIC-Plus)

This scale is designed to measure various domains that describe subject function: general, mental/cognitive state, behavior, and activities of daily living. The CIBIC-Plus scores will be assigned by clinicians and the possible scores are: 1 (marked improvement), 2 (moderate improvement), 3 (minimal improvement), 4 (no change), 5 (minimal worsening), 6 (moderate worsening) and 7 (marked worsening).

Neuropsychiatric Inventory (NPI)

This scale assesses frequency and severity of 12 neuropsychiatric symptoms commonly described in dementia patients: delusions, hallucinations, agitation/aggression, depression/dysphoria, anxiety, elation/euphoria, apathy/indifference, disinhibition, irritability/lability, motor disturbance, nighttime behaviors and appetite/eating changes. The scale is composed of 12 items, each item score ranges from 0 to 12.

The NPI Total Score (range 0 to 144) = sum of all item scores. If any item score is missing it is set to zero. The higher the total score, the more severe the symptoms.

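### The Full Analysis Set is defined by the MoCA but used for all nine efficacy scales, so a treated subject with no MoCA at any post-baseline visit also drops out of the clinician- and caregiver-rated summaries

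*SAP*

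**What the plan says.** SAP 5.2.1, with the same wording in protocol 9.7.1.2, admits to the FAS subjects who took at least one dose and "have baseline and at least 1 post baseline MoCA measurement".

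That set serves every efficacy scale. SAP 5.8 names MoCA, WAIS-IV DSC, CIBIC-Plus, CGIC, CFI, MMSE and NPI, and its list ends "SAPS-PD and FAQ, will be summarized based on the FAS, by subject subgroup". Protocol 9.7.1.6 agrees: "The exploratory efficacy endpoints will be summarized based on the FAS".

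On missing values, SAP 8.4 says of the MoCA, "If any assessment is missing, then the Total Score is missing", and SAP 5.3.5.1 adds, "For the efficacy endpoints, there will be no imputation of missing value".

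On timing, protocol 9.1.2.1 says "Efficacy assessments will be performed after 6 and 12 weeks on E2027". For subjects who stop early, protocol 9.3.3 says "The safety and efficacy assessments normally performed after 12 weeks of treatment will be conducted at the ED Visit". The schedule (protocol Table 5) also allows a MoCA at unscheduled visits, and SAP 5.3.5.1 brings post-ED data into the analyses.

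Neither document gives an endpoint-specific analysis set, or a supplementary summary for subjects who have other post-baseline ratings but no MoCA.

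**The concern.** Membership of the analysis set for nine scales depends on having a value of one of them, and that one is a performance test. CGIC is the clinician's own judgement on all available information (protocol 9.5.1.2.8). The caregiver supplies NPI, CFI, SAPS-PD and FAQ and contributes to CIBIC-Plus (protocol 9.1.2.1). None of these needs a completed MoCA. In DLB or PDD, inability to do a cognitive test may reflect the disease getting worse, so the exclusion can depend on outcome. The ratings that would record the decline could then be discarded for want of a different measurement.

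These endpoints get no formal testing (SAP 5.8), so the descriptive tables and figures carry the efficacy information. Protocol 7.3 says that the pattern of cGMP and efficacy response with and without amyloid will guide the choice of subgroups for Phase 3. With about eight subjects per subgroup, one subject is visible in that pattern.

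**Working it through.** **1. Subgroup sizes.** Inputs from SAP 4: SD 60, difference 100 (percentage points of CSF cGMP change), power about 80%, dropout 25%. Alpha is not stated there; two-sided 0.05 is assumed.
- n per subgroup = 2 × (1.960 + 0.842)² × (60/100)² = 5.65, rounded up to 6.
- Enrolled = 6/(1 − 0.25) = 8 per subgroup, and 4 × 8 = 32 treated.
- Normal-approximation power at n = 6 is 82.3%.
- The standard error is 60 × √(2/6) = 34.64. P(observed difference ≥ 30) is 97.8%, 80.7% and 28.2% for true differences of 100, 60 and 10, as the SAP states.

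The plan's figures reproduce. They concern cGMP only and are used here just for the denominators 8 and 6.

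**2. Who is removed.** Applying the rules to five kinds of treated subject:
- MoCA done at Week 6 but not at Week 12: in the FAS, and all the Week 12 ratings on other scales count.
- Every MoCA component attempted, very low score: in the FAS.
- Only a partial MoCA after baseline, total set to missing: undetermined, because the SAP does not say whether this is a MoCA measurement.
- Stops before Week 6, MoCA not done at the ED Visit or later, but clinician or caregiver ratings taken: out of the FAS, and those ratings are dropped from every efficacy summary.
- Leaves with no post-baseline efficacy visit: out of the FAS, but there is nothing to recover.

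The fourth case is the problem and the third is an ambiguity. Under SAP Table 3, ratings from an ED Visit in the fourth case would otherwise appear under Week 6 (under Week 12 for SAPS-PD and FAQ, which have no Week 6 assessment) and as the end-of-treatment value.

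**3. Weight of one subject.**
- Share of a subgroup: 1/8 = 12.5%; 1/6 = 16.7%.
- For two subjects: 2/8 = 25%; 2/6 = 33%.
- An early discontinuer is not a completer, so 8 is the natural denominator. Six shows the effect when only six subjects have ratings.

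**4. Illustration on CIBIC-Plus.** Assumption, not from the documents: everyone else scores 4 (no change) and the excluded subject scores v. The FAS mean is 4.00. The mean over all rated subjects is ((N − 1) × 4 + v)/N.
- N = 8: v = 5, 6, 7 gives 4.13, 4.25, 4.38.
- N = 6: v = 5, 6, 7 gives 4.17, 4.33, 4.50.
- Share rated worse: 12.5% (N = 8) or 16.7% (N = 6), against 0% in the FAS.

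**5. How often.** The documents give no rate of having no post-baseline MoCA. If the per-subject probability p were 2%, 5% or 10% (assumed range), the chance of at least one such subject among 32, 1 − (1 − p)³², is 48%, 81% or 97%. Within one subgroup of 8 it is 15%, 34% or 57%. The range shows only that the answer depends on p.

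**6. Direction.** Dropping a decliner flatters the mean of that subject's own subgroup. If that is a with-amyloid subgroup, the contrast with its without-amyloid counterpart shrinks, against the trial's hypothesis. If it is a without-amyloid subgroup, the contrast widens in the hypothesis's favour. If the MoCA is missing for reasons unrelated to decline, no direction follows.

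**The case against.** The strongest reply is that the trigger is narrow. A subject must lack a MoCA at every post-baseline opportunity, and severe impairment normally gives a low score. SAP 8.4 treats inability or unwillingness as missing for the WAIS-IV DSC but says nothing like it for the MoCA, and MoCA subitems are summarised too, so a partial test may qualify. MoCA, CIBIC-Plus, CGIC, NPI and CFI share the same visits, so many dropouts will lack all of them. CIBIC-Plus also needs an interview with the subject (protocol 9.5.1.2.3). All this stands and limits how often the problem can arise. It gives no reason to discard ratings that were obtained.

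It is also true that deterioration stays visible elsewhere. Adverse events and UPDRS-III are reported on the Safety Analysis Set, and discontinuation reasons on treated subjects. The primary cGMP analysis uses the PD Analysis Set, and the biomarker–efficacy correlations in SAP 5.5.2 name no FAS restriction.

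Three stronger readings are tempting, and the documents support none of them:
- A reader might infer that anyone who becomes too impaired for the MoCA is removed. A Week 6 MoCA keeps the subject in.
- A reader might infer a bias in favour of E2027, citing worsening of DLB in Study 201 (5.1% against 1.0% on placebo, protocol 7.2). That is an adverse-event incidence, and nothing links those subjects to missing MoCAs. The same section gives severe events of 2.0% against 6.2% on placebo, and protocol 9.5.5 reports no discontinuations for adverse events.
- A reader might set a one-subject shift in a subgroup's NPI mean beside the Study 201 with-amyloid difference of −2.757. That figure is a model-based difference from placebo with a 95% CI of −10.095 to 4.581, not a within-subgroup mean change.

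**Conclusion.** The point holds in this form: the FAS rule can remove existing clinician- and caregiver-rated data from the efficacy summaries because a different scale was never measured after baseline. The most plausible case is a subject who discontinues before Week 6 and cannot do the MoCA at the ED Visit. The exclusion can depend on outcome, but its frequency is undocumented and its direction is not established.

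One such subject carries an eighth to a sixth of a subgroup. The CIBIC-Plus shift of 0.13 to 0.38 at N = 8 rests on the assumption that all others score 4, and shows scale only. Severity is low: the affected summaries are exploratory and descriptive, and the primary analysis, adverse events and UPDRS-III do not use the FAS.

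**What to change.** Three edits to SAP 5.2.1 and 5.8, with matching wording in protocol 9.7.1.2 and 9.7.1.6:

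1. Summarise each efficacy endpoint in treated subjects with a baseline value (where the scale has one; CIBIC-Plus and CGIC need only a post-baseline rating) and at least one post-baseline value of that endpoint. If the sponsor prefers to keep the FAS as it is, add this as a supplementary summary.
2. State whether a partly completed MoCA with a missing total counts as a MoCA measurement.
3. Report, by subgroup, how many treated subjects have no post-baseline MoCA, and why.

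The cost is a few sentences and one small table. No new data are collected and no MoCA result changes. Denominators may differ between scales, so each table should print its own n.
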